8.5. Suspected PD Visit (Any Time)

The following procedures will be performed when Disease Progression is suspected:

- Adverse events
- Concomitant medications
- Study drug compliance review
- Physical exam
- Vital signs
- ECOG
- CT/MRI scan (For confirmation of PD)
- Bone marrow biopsy/aspirate as clinically indicated
- Overall response assessment
- Hematology
- Serum chemistry
- ██████████ assays (MRD and FD cohort, including with bone marrow biopsy when obtained)

8.6. Suspected CR Visit

The following procedures will be performed (along with regularly scheduled study assessments) when Complete Response by imaging is suspected:

- Bone marrow biopsy and aspirate (for CR confirmation)
- ██████████ assays (MRD cohort only)
- MRD assessment (by PB and bone marrow aspirate)

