- If the bone marrow biopsy and aspirate results demonstrate a hypocellular marrow, a repeat biopsy (in 4 weeks up to 6 months) is needed per IWCLL Guidelines (see Section 7.2.3.2)

Table 10. Fixed Duration cohort: Bone Marrow Biopsy and Aspirate Collection Times for Clinical Response

	Screening Visit	C10 (±14 days)	C19 (3 mo after completion of C15 combo [±14 days])	Suspected CR Visit	Suspected PD Visit
BM Biopsy (local and central lab)	X (local only)	X ^{a,c,d}	X ^{a,d}	X ^{a,d}	X ^b
BM Aspirate (local and central lab)		X ^{a,c,d}	X ^{a,d}	X ^{a,d}	X ^b

- BM biopsy and aspirate for clinical response assessment (local lab and ██████████ central lab); BM aspirate used for MRD assessment, and ██████████ studies (MRD central lab)
- Only required to document PD by cytopenic progression, as appropriate (local lab)
- Unless collected prior and within 3 months for CR assessment, and confirmed CR and MRD-negative in BM
- If the bone marrow biopsy and aspirate results demonstrate a hypocellular marrow, a repeat biopsy (in 4 weeks up to 6 months) is needed per IWCLL Guidelines (see Section 7.2.3.2)

At Screening (MRD and FD Cohorts)

A unilateral bone marrow biopsy must be obtained at Screening or up to 90 days before enrollment for disease confirmation.

The following material will be sent to the central laboratory:

- Bone marrow trephine (≥ 1 cm) in a container of neutral buffered formalin (no other fixative allowed); NOTE: The bone marrow trephine will be split in half with one portion to remain at the site for local assessment and the other half sent to the central laboratory
- Bone marrow aspirate

If insufficient marrow biopsy material or slides are available to be submitted, high resolution images of the available representative slides should be acquired and submitted instead.

Copies of redacted bone marrow pathology reports for samples reviewed locally will be collected and may be reviewed by the Sponsor and/or IRC.

For Response Evaluation (MRD and FD Cohorts)

At every Overall Response Assessment with a scheduled BM evaluation ([Table 9](#) for MRD cohort and [Table 10](#) for FD cohort), or if the subject's physical examination findings, laboratory evaluations, and radiographic evaluations suggest that CR has been achieved in all response parameters at other time points (Suspected CR), a bone marrow aspirate and biopsy must be obtained to confirm the CR and to evaluate minimal residual disease.

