7.2. Efficacy Evaluations

Clinical disease evaluations will include:

- Physical examination (which will focus on the presence/absence of size increase/decrease in lymph nodes, liver, and spleen)
- Hematologic parameters by CBC performed at a local laboratory
- Radiographic evaluation (CT or MRI scan of the neck, chest, abdomen, and pelvis)
- Bone marrow biopsy (as appropriate) if there is evidence of CR in the other response parameters

If study drug is held before a scheduled clinical response assessment, then the response assessment can be delayed up to 4 weeks to allow re-initiation of study drug for 2 weeks (or as long as possible) prior to performing scheduled response assessment.

Clinical efficacy assessments, for the purpose of the study result analyses, will be performed by Investigators. For response assessments not requiring a CT scan, the Investigator should evaluate response based on available clinical data, including physical examination and laboratory results. For the MRD and Fixed Duration cohorts, imaging will be collected and stored centrally. The Sponsor may utilize IRC for independent review of efficacy with details to be outlined in the separate IRC charter.

MRD Evaluations:

Samples for MRD analysis will be sent to a central laboratory that has a validated flow cytometry assay that has a limit of detection of 10^{-4} . MRD will be assessed in the following compartments:

- Bone marrow
- Peripheral blood

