7.2.3.1. Complete Response (CR)

All of the following are required for a CR:

- No significant lymphadenopathy (>1.5cm) palpable on examination or by CT
- No hepatosplenomegaly on examination or by CT
- No constitutional symptoms (ie, no fever >38°C for ≥2 weeks, no ongoing unintentional ≥10% body weight loss, no night sweats for >1 month without other evidence of infection, no fatigue interfering with work or usual activities) attributable to CLL.
- Neutrophils >1500/μL, platelets >100,000/μL, and Hgb >11g/dL without recent growth factor or transfusions
- ALC <4,000/μL

Marrow aspirate and biopsy must be performed after all other criteria meet the definition of CR. To define a CR, the marrow sample must be at least normocellular for age, with less than 30% of nucleated cells being lymphocytes. B-lymphoid nodules should be absent.

In addition, in subjects with a CR, MRD should be performed on both peripheral blood and bone marrow aspirate to evaluate MRD status.

Table 15. Criteria for Clinical Response Categories

Parameter	CR	PR	PD
Group A			
Lymphadenopathy ^a	None; ≤1.5cm	Decrease ≥50%	increase ≥50%
Hepatomegaly	None	Decrease ≥50%	increase ≥50% or new hepatomegaly
Splenomegaly	None	Decrease ≥50%	increase ≥50% or new splenomegaly
Blood lymphocytes	<4000/μL	Decrease ≥50% from baseline	increase ≥50% over baseline ^c
Marrow ^b	Normocellular, <30% lymphocytes, no B lymphoid nodules. Hypocellular defines CRi ^d in a patient with cytopenias		
Group B			
Platelet count	>100,000/μL	>100,000/μL or increase ≥50% over baseline	Decrease of ≥50% from baseline secondary to CLL
Hemoglobin	>11 g/dL	>11 g/dL or increase ≥50% over baseline	Decrease of >2g/dL from baseline secondary to CLL
Neutrophils	>1500/μL	>1500/μL or increase ≥50% over baseline	N/A

- Sum of the products of multiple lymph nodes (as evaluated by CT scans) or the longest diameter of one target lymph node
- This parameter is not relevant for the PD category unless confirming cytopenic progression.
- Subjects with treatment-related lymphocytosis should remain on study treatment in the absence of other criteria for progressive disease (see [Section 7.2.1.2](#)).
- Hypocellular marrow is a CRi when peripheral blood cytopenias not meeting Group B criteria are present. CRi requires at least one abnormal Group B criteria.

Note: Group A defines the tumor load and Group B defines the function of the hematopoietic system

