7.2.3.2. Complete Response with an Incomplete Marrow Recovery (CRi)

Complete response with an incomplete marrow recovery (CRi) is defined as a CR with an incomplete recovery of the subject's bone marrow, manifested by persistent cytopenias. Subjects who have a CRi fulfill all criteria for a CR, but continue to have persistent anemia, thrombocytopenia, or neutropenia. These cytopenias are due to drug toxicity in the bone marrow and are not due to any evidence of CLL. If the marrow is hypocellular, a repeat determination should be performed after 4 weeks, or when peripheral blood counts have recovered. However, this time interval should not exceed 6 months.

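### Protocol 8.6 conflicts with 7.1.3.3, 7.2 and 7.2.3.1 on what triggers the unscheduled marrow, and the all-parameters trigger can never be met by a CRi candidate

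*Protocol*

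**What the plan says.** Four protocol sections say when a marrow outside the fixed schedule is taken to establish complete response.

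- **8.6, Suspected CR Visit:** the marrow and MRD samples are "performed (along with regularly scheduled study assessments) when Complete Response by imaging is suspected". No blood-count condition is attached.
- **7.1.3.3, response evaluation:** apart from the scheduled marrows, one is required if the physical examination, "laboratory evaluations, and radiographic evaluations suggest that CR has been achieved in all response parameters at other time points (Suspected CR".
- **7.2, Efficacy Evaluations:** marrow biopsy is done "if there is evidence of CR in the other response parameters".
- **7.2.3.1, Complete Response:** "Marrow aspirate and biopsy must be performed after all other criteria meet the definition of CR". The listed criteria include neutrophils above 1500/μL, platelets above 100,000/μL and "Hgb >11g/dL without recent growth factor or transfusions".

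Protocol 7.2.3.2 describes CRi subjects as meeting CR "but continue to have persistent anemia, thrombocytopenia, or neutropenia", and note d to Table 15 requires at least one abnormal Group B count. Protocol 7.2.2 requires marrow confirmation of CR. The FD primary endpoint is a best overall response of CR or CRi (Protocol 10.2.2; SAP Table 2).

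**The concern.** CRi is one of the two responses that make up the FD primary endpoint, and the protocol gives two incompatible rules for when to look for it outside the schedule. A subject with complete nodal and organ response on CT but low counts gets an unscheduled marrow at a site that follows 8.6. At a site that follows 7.1.3.3 the same subject does not. Whether and when that subject becomes a CRi could therefore depend on which section the site reads. At stake are the CR/CRi rate in both cohorts and two supportive FD analyses that start from the CR/CRi date: duration of complete response (DOCR) and durable CRR.

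**Working it through.** **1. Can a CRi candidate meet each trigger?**

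| Section | Condition on Group B counts | Can a CRi candidate meet it? |
|---|---|---|
| 8.6 | none (imaging) | yes |
| 7.1.3.3 | laboratory values must suggest CR in all parameters | no |
| 7.2 | all other parameters show CR | no |
| 7.2.3.1 | all three counts above threshold | no |

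CR needs all three Group B counts above threshold, and CRi needs at least one that is not. No subject satisfies both at once, so the last three triggers exclude CRi by construction.

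**2. What other route leads to a marrow?** Protocol 7.1.3.3 offers the scheduled evaluations as an alternative to Suspected CR. Compare the CT visits (Protocol 8.2.1.6 to 8.2.2, 8.3.1.5 to 8.3.2; Appendices A and B) with the marrow schedule (Tables 9 to 12).

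| Cohort | CT visits | Scheduled marrow | CT without scheduled marrow |
|---|---|---|---|
| FD, C7 to C31 | C7, C10, C13, C19, C25, C31 | C10, C19 | 4 of 6: C7, C13, C25, C31 |
| MRD, C10 to C35 | C10, C16, C23, C29, C35 | C16, C29 | 3 of 5: C10, C23, C35 |

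These visits are not equally exposed. FD C7 and C13 are followed by the C10 and C19 marrows, and MRD C10 and C23 by the C16 and C29 marrows. At those visits only the date is at risk. Detection is at risk at FD C25, C31 and the annual CTs, and at MRD C35 and later. It is also at risk for subjects who miss a scheduled marrow. Early discontinuers are an example: Protocol 8.8 lists no marrow in response follow-up, although 8.3 keeps FD subjects on the same visit schedule.

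**3. Dating.** Day 1 of cycle k is study day 28(k − 1) + 1.

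- C7D1 = 169 and C10D1 = 253: a shift of 84 days.
- C13D1 = 337 and C19D1 = 505: a shift of 168 days.
- C31D1 = 841, which is where the minimum FD follow-up of 30 cycles ends (SAP 1.5.2).

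Durable CRR needs DOCR of at least 336 days (SAP Table 2). For the last-enrolled subject, at C31D1:

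- CRi dated at C13: 841 − 337 = 504 days.
- CRi dated at C19: 841 − 505 = 336 days, exactly the threshold.
- CRi dated by a C19 marrow taken at the late end of its 14-day window: 336 − 14 = 322 days, below the threshold.

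This assumes that CRi is dated by the marrow. The SAP starts DOCR at the initial CR or CRi but does not say which assessment supplies that date.

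**4. The plan's power figure.** Inputs from Protocol 10.3 and SAP 1.4: n = 125, null 37%, alternative 50%, one-sided alpha 0.025. With the variance at the alternative, power = Φ[(0.50 − 0.37)√125 / √(0.50 × 0.50) − 1.96] = Φ(0.947) = 82.8%, which reproduces the stated 83%. The calculation stops there. Neither document gives the expected CRi share, or the share of CRi that would depend on an unscheduled marrow, so no change in rate or power can be derived.

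**The case against.** The strongest reply is that the plan nearly always takes the marrow anyway. FD marrows at C10 and C19 are due whatever the counts. The C10 marrow is waived only if one within the prior 3 months already showed CR and marrow MRD negativity. The endpoint is best overall response, so a CRi found at either visit counts. The Suspected CR column of Tables 9 and 10 also carries a hypocellular-marrow footnote that points to 7.2.3.2, so the authors evidently expected this marrow to identify CRi. All of this stands, and it confines the problem.

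Several stronger readings may tempt a reader, and the documents do not support them.

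- *A cytopenic CRi candidate gets no marrow and is lost from the FD primary endpoint.* The C10 and C19 marrows contradict this as a general statement. A subject whose counts later recover would also meet the all-parameters trigger.
- *Even a scheduled marrow taken while counts are low is out of order.* The sentence in 7.2.3.1 governs CR. CRi has its own definition, and 7.2.3.2 allows a hypocellular marrow to be repeated once counts recover, which implies that the first was taken while they were low.
- *The venetoclax monotherapy cytopenia rates in 1.3.2.2 (41.0%, 28.8%, 20.7%) size the problem.* They are adverse-event incidences, not counts at the time of CT response. C25D1 is also 673 − 421 = 252 days after FD treatment ends, and 7.2.3.2 attributes CRi cytopenias to drug toxicity.
- *The FD test loses power by a known amount.* One subject is 1/125 = 0.8 points, and power would be 76.5% if the true rate were 49%. Nothing in the documents says that any such loss occurs.

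One part of the defence does not succeed. Appendix B footnote i allows marrow to evaluate cytopenia, but this is discretionary and sets no response trigger. Elsewhere in 7.1.3.3 such marrows serve suspected progression or the cause of the cytopenia.

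**Conclusion.** The conflict is real. Three sections state a trigger that CRi cannot meet, and 8.6 states one that it can. The consequence is narrow:

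- CRi first evident after the last scheduled marrow (FD C19, MRD cohort C29);
- subjects who miss a scheduled marrow;
- the date of a CRi first seen at FD C7 or C13, which can shift by 84 or 168 days and so affect DOCR and durable CRR, provided CRi is dated by the marrow and the cytopenia persists to the next scheduled marrow.

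The effect on the CR/CRi rate cannot be sized from the documents. Any missed CRi lowers the observed rate, so the FD test becomes conservative and its type I error is not inflated. The sample-size calculation is not in error.

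**What to change.** Reconcile Protocol 8.6, 7.1.3.3, 7.2 and 7.2.3.1 to a single response-assessment trigger that covers CRi candidates. For example, take the marrow when lymph nodes, liver, spleen, ALC and constitutional symptoms meet CR, whatever the neutrophil, platelet and hemoglobin values, and classify CR or CRi afterwards from the counts and the marrow. Name these parameters one by one. Writing Group A instead would be circular, because Table 15 lists marrow within Group A.

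The cost is protocol wording. The example trigger adds ALC and symptoms to the imaging condition, so it is narrower than 8.6 and orders no marrow that 8.6 does not already order.

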8.7. End-of-Treatment Visit

The following will be performed 30 (\pm 3) days after discontinuation of therapy (if the assessments do not coincide with regularly scheduled study assessments) or at start of new anticancer therapy, whichever occurs earlier. For the Fixed Duration Cohort, if subject completes fixed duration regimen, this visit will take place at Cycle 17 Day 1.

- Adverse events
- Concomitant medications
- Study drug compliance review
- Physical exam
- Vital signs
- ECOG
- Hematology
- Serum chemistry
- MRD (peripheral blood)
- ██████████ assays (MRD cohort only)

Subjects that withdraw from treatment for reasons other than clinical progressive disease in either cohort should continue to participate in ongoing Response Follow-Up visits until confirmed disease progression.

8.8. Response Follow-Up Visits

Subjects who discontinue treatment for reasons other than disease progression will continue to come in every 3 months (or per assigned treatment schedule) until disease progression or study closure, whichever is earlier. Subjects will undergo the following procedures:

- Physical exam
- Vital signs
- ECOG
- Hematology
- Serum Chemistry

- MRD (peripheral blood) every 6 months for one year, then annually thereafter until initiation of subsequent anti-cancer therapy
- Overall Response Assessment
- CT/MRI scan (every 6 months for one year, then annually thereafter)
- Other malignancies
- Any subsequent anti-cancer therapy

If an alternative anti-cancer therapy is initiated, response to all subsequent anti-cancer therapies including best overall response for each regimen, whether the subject progressed following each regimen, and date of PD if applicable will be assessed.

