8.2.2. Cycle 17 Randomization Visit and Every 3 Cycles Thereafter

The following procedures will be performed on Day 1 (± 3 days) of Cycles 17 and every 3 cycles thereafter (unless indicated otherwise) until disease progression, unacceptable treatment-related toxicity, or other reasons outlined in [Section 9.2](#):

Pre-Dose

- Adverse events
- Concomitant medications
- Study drug compliance review
- Physical exam
- Vital signs
- ECOG
- Hematology
- Serum chemistry
- CT/MRI (Cycle 23, Cycle 29, Cycle 35, and then annually thereafter)
- Overall response assessment
- Bone marrow biopsy (± 14 days from C29 unless collected prior for CR assessment, and confirmed MRD-negative in BM)
- MRD assessment (by PB starting Cycle 20, 23, 26, 29, and every 6 cycles thereafter; by bone marrow aspirate [BMA] at Cycle 29 in randomized subjects, and in any subject with MRD-neg conversion in PB; BMA can be drawn ± 14 days from C29D1.)
- ██████████ assays ██████████

Post-Dose

- Dispense randomization specific study medication to subject for off-site use and provide study drug compliance instructions

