## **1.4. Sample Size Determination**

### **MRD Cohort**

The MRD cohort is powered based on the primary endpoint of randomization phase, 1-year DFS rate in MRD-negative randomized subjects (ibrutinib vs placebo). The total sample size will be based on both MRD negativity rate from the Pre-randomization Phase and the sample size assumption from Randomization Phase.

Sixty randomized subjects with confirmed MRD negativity will provide approximately 80% power to detect a 30% improvement in the 1-year disease-free rate, assuming the 1-year disease-free rate is 60% for the control (placebo) arm, at a 2-sided significant level of 0.05.

Assuming a 40% MRD negativity rate for the ibrutinib and venetoclax combination therapy in the Pre-randomization Phase, 150 subjects will be enrolled in the Pre-randomization Phase in order to have 60 subjects achieve confirmed MRD negativity and to be randomized.

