## 1.6. Testing Procedure and Level of Significance

For both cohorts, hypothesis testing will be performed independently (without multiplicity adjustment) for the primary endpoint only. Other endpoints will be summarized descriptively with 95% confidence interval (CI) whenever applicable.

- Primary endpoint for MRD cohort, 1-year DFS rate in MRD-negative randomized subjects, will be tested between placebo and ibrutinib arms at a 2-sided alpha level of 0.05.
- Primary endpoint for FD cohort, CRR, will be tested in non-del 17 subjects at a 1-sided alpha level of 0.025.

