### **1.7.2. Randomization Method**

After completing the 12 cycle Ibr + Ven treatment in MRD cohort, subjects will be randomized centrally by two separate schemes according to MRD status, each stratified by IGHV status (Unmutated vs mutated [including borderline or not evaluable]):

- Subjects who achieve confirmed MRD negativity are to be randomized to receive double blind study treatment, either placebo or ibrutinib.
- Subjects who do not achieve confirmed MRD negativity are to be randomized to receive open label treatment, either single agent ibrutinib or Ibr + Ven.

In each scheme, subjects will be randomized in a 1:1 ratio within each randomization stratum. This randomization scheme will be implemented within the IRT system.

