**Table 2: Definitions and Analyses for Endpoints**

Endpoint	Definition	Analysis Method
Primary Endpoint for MRD Cohort (Not Applicable for FD cohort)		
1-year DFS rate in MRD-negative randomized subjects	DFS will be analyzed in MRD-negative randomized subjects and is defined as time from randomization date to MRD-positive relapse [1], or disease progression per investigator assessment or death from any cause, whichever occurred first. Subjects who do not experience any DFS event will be censored by the last MRD sample date with a valid result [2] or the date of last adequate disease assessment [3] after randomization, whichever occurs earlier. If no valid MRD result and no adequate disease assessment after randomization, DFS will be censored on the randomization date.	
Primary
 
The 1-year DFS rates will be estimated using Kaplan-Meier method and the corresponding 2-sided 95% CI will be provided. Z test for the difference of two proportions will be performed based on Kaplan-Meier estimates with standard error of each arm computed using Greenwood's formula.
 
Supportive
 
A log-rank test will be performed for between-arm comparison of DFS distribution. The hazard ratio and its 95% CI based on Cox regression model will be calculated. The 2-year DFS will be explored when median follow-up post randomization <math>\geq 2</math> years.

Endpoint	Definition	Analysis Method
Primary Endpoint for FD Cohort (Secondary Endpoint for MRD cohort)		

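### Protocol 8.8 and Appendix A disagree on blood MRD sampling after blinded drug is stopped; following 8.8 roughly halves sampling in the primary-endpoint year for subjects who stop

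*Protocol*

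**What the plan says.** On randomized treatment, Protocol 8.2.2 schedules blood MRD "by PB starting Cycle 20, 23, 26, 29, and every 6 cycles thereafter". With 28-day cycles, the first four samples fall on days 84, 168, 252 and 336 after C17D1, and the next is C35, day 504.

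For subjects who stop without progression, Protocol 8.8 sets 3-monthly visits, or visits on the assigned treatment schedule. Its MRD item carries its own interval: "MRD (peripheral blood) every 6 months for one year, then annually thereafter until initiation of subsequent anti-cancer therapy". Section 8.8 serves both cohorts.

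The appendices differ from each other. In Appendix A (MRD cohort), the 3-monthly Response Follow-Up column has a plain blood-MRD mark, although the CT cell in that column carries a reduced frequency. In Appendix B (Fixed Duration cohort), the MRD cell carries the same 6-monthly-then-annual frequency as 8.8.

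SAP Table 2 counts MRD-positive relapse as a DFS event. A subject without an event is "censored by the last MRD sample date with a valid result" or at the last adequate disease assessment, whichever is earlier. Stopping drug is not a censoring reason, and SAP 2.1 analyses subjects as randomized. The 1-year rate "will be tested between placebo and ibrutinib arms at a 2-sided alpha level of 0.05".

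**The concern.** Two parts of the protocol give different instructions for measuring a component of the primary endpoint. A site following 8.8 and a site following Appendix A would sample the same subject at different rates.

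Under 8.8, how intensively relapse is looked for in the primary-endpoint year depends on whether the subject still takes blinded drug. Sparser sampling can date a relapse later, move it past the 1-year landmark, or move the censoring date earlier. If one arm stops more often, these effects fall more on that arm. One arm takes active drug with toxicity-based discontinuation rules (Protocol 5.4.1.4), so different stop rates are plausible.

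**Working it through.** **1. The plan's own figure.** SAP 1.4 states: "Sixty randomized subjects with confirmed MRD negativity will provide approximately 80% power to detect a 30% improvement in the 1-year disease-free rate". The placebo rate there is 60%, so the target for ibrutinib is 90%. Allocation is 1:1 (SAP 1.7.2), so 30 per arm. The test is a z test with per-arm Greenwood standard errors (SAP Table 2), which corresponds to an unpooled variance:

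- SE = sqrt((0.60×0.40 + 0.90×0.10)/30) = sqrt(0.33/30) = 0.105
- Power = Φ(0.30/0.105 − 1.96) = 81.6%; total N for 80% = 58

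The stated power reproduces (a pooled variance gives 78.0%). The useful scale is a standard error of about 10.5 points, and one subject is 1/30 = 3.3 points of an arm's rate.

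**2. Number of samples.** On drug there are four scheduled blood samples in 365 days. After an early stop, 8.8 gives about two a year plus the End-of-Treatment sample at about 30 days (Protocol 8.7). The 3-monthly reading of Appendix A gives about four plus that sample.

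**3. Share of relapses found by month 12, by stop month s.** Assume relapse is uniform from s to month 12 and the 6-month clock starts at the stop. Day 336 is month 11.04.

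- 8.8: 6/(12−s) for s up to 6. For s = 7 to 9 only the End-of-Treatment sample falls before month 12, giving 1/(12−s).
- C20-C29 schedule: (11.04−s)/(12−s).

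| Stop month | 8.8 | C20-C29 |
|---|---|---|
| 1 | 55% | 91% |
| 2 | 60% | 90% |
| 3 | 67% | 89% |
| 4 | 75% | 88% |
| 5 | 86% | 86% |
| 6 | 100% | 84% |
| 7 | 20% | 81% |
| 8 | 25% | 76% |
| 9 | 33% | 68% |

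The gap depends on the stop month and reverses at month 6. It also depends on the anchor. Protocol 8.2 anchors MRD-cohort visits to C1D1. If the 6-monthly samples fall on C23 and C29, the last sample before the landmark is C29, as on drug, and the landmark loss is zero.

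**4. Hand estimate for stops at months 1-4.** With 10% of an arm stopping, 10-40% of them relapsing and a detection gap of 13-36 points (88−75 to 91−55): 0.10 × (0.10 to 0.40) × (0.13 to 0.36) = 0.1 to 1.4 points. In an arm of 30 that is 3 stoppers and 0.04 to 0.43 of one subject.

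**5. Simulation.** Assumptions: all DFS events are MRD relapses, times are exponential, true 1-year DFS is 60% and 90%, stops are uniform over the first 336 days, and the event is dated at the first positive sample. Off drug, both schedules run from the stop date and include the 30-day sample. Mean delay from relapse to first positive sample in stoppers is about 82 days under 8.8 and 39 days under 3-monthly sampling. The table shows the shift in the ibrutinib-minus-placebo difference (8.8 minus 3-monthly, in points). The first results column carries simulation noise of about 0.1.

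| Stops, placebo / ibrutinib | Hazard unchanged after stopping ibrutinib | Hazard rises to placebo level |
|---|---|---|
| 5% / 10% | about 0 | +0.3 |
| 5% / 20% | −0.1 | +0.7 |
| 5% / 30% | −0.1 | +1.15 |
| 0% / 30% | not run | +1.35 |
| 20% / 20% | −0.5 | +0.1 |
| 20% / 5% | −0.9 | −0.6 |

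The simulation takes follow-up to day 365 as complete. It does not model the earlier-of-two-dates censoring rule or the requirement for a confirming sample.

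**The case against.** A reader might infer that the plan ascertains the primary endpoint unequally between arms. The documents do not support that. Section 8.8 applies identically to both blinded arms, sampling depends on drug status, and no by-arm stop rate is given. Subjects who had already discontinued ibrutinib are not eligible for randomization (Protocol 3.1.1), so those randomized have stayed on it for about 16 cycles and may stop less often. This objection stands.

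A reader might also infer that any such effect must favour the arm with more stops. That does not follow either. Earlier censoring removes a subject from the Kaplan-Meier risk set without counting the subject as disease-free, and it biases the estimate only if it is informative. Because relapse is more frequent on placebo, equal stopping can shift the difference slightly against ibrutinib.

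Three mitigations are real but partial:

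- The End-of-Treatment sample exists, but for stops at months 1-4 it leaves the landmark percentages unchanged, because the 6-month sample would find the same relapses.
- An any-time visit is available (Protocol 8.2.3), but only once relapse is suspected. Since Protocol 7.2.1.4 describes MRD as invisible to routine imaging and laboratory tests, that visit mainly speeds confirmation.
- The allowance for visits on the assigned schedule governs attendance, while the MRD item states its own interval. If it is read as overriding that interval, sites could still differ.

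The 8.8 interval may be Fixed Duration wording carried into a shared section, since Appendix B matches it. That would explain the conflict but not resolve it.

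**Conclusion.** The inconsistency holds and should be reconciled; its severity is minor. If 8.8 is followed, subjects who stop blinded drug in the primary-endpoint year are sampled about half as often as those on drug, apart from one End-of-Treatment sample. The contrast runs only through C29, because on-drug sampling then falls to every 6 cycles (168 days).

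If stopping differs by arm, MRD relapse can be found later, or DFS censored earlier, in one arm. Under the assumed stop rates of 0-20% on placebo and 5-30% on ibrutinib, the shift in the 1-year difference is about −0.9 to +1.4 points. Where stops are more common on ibrutinib, it is about 0 to 1.4 points in ibrutinib's favour. This is small beside the 30-point design difference and the 10.5-point standard error, although a single missed relapse moves an arm by 3.3 points. Direction and size depend on when drug is stopped, on relapse risk after stopping, and on the anchor of the 6-month clock, which 8.8 does not state.

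**What to change.** Amend 8.8 to state that MRD-negative randomized subjects keep blood MRD at the C20, C23, C26 and C29 timepoints whether or not blinded drug continues, and that the 8.8 frequency applies only after C29. Annotate the Appendix A Response Follow-Up cell to match, and state the anchor for the later 6-monthly samples.

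The cost is amendment wording and one or two extra central-laboratory blood samples per early stopper, drawn at 3-monthly visits that already include hematology and chemistry. If those visits have already passed, reconcile the text and report MRD sampling after discontinuation by arm alongside the DFS result.
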